#### **Return of Results**

All findings: Follow up with the patient's family of testing results will be guided by the clinical care team. All subjects who receive results as a part of this study may be offered the opportunity to follow-up with licensed genetic counselors and/or medical staff from the genome institute to discuss the return of results in-person. This post-test genetic counseling will be available to all subjects as a part of this study and may be done in the in-patient setting, over the telephone or other telecommunication device, or in an out-patient setting. These post-test counseling visits will be documented in the subject's RCHSD EHR, but there will not be any billing or charges associated with these visits. All genetic counseling sessions (including any pre-test counseling, generation of a pedigree, or post-test follow-up contact) with our licensed research team will be documented in the patient's EHR to facilitate communication amongst clinical teams. Such sessions are in addition to any clinically indicated counselling or testing which will be performed and billed as appropriate by the clinical genetics team and other clinical providers. If the findings pertain to someone who is not a patient in the hospital system, in addition to our counselling, we will ask the subject to identify a provider to whom the results can be

returned.

**Primary findings:** Pathogenic and likely pathogenic variants (as determined by ACMG guidelines) that relate in part or in whole to the patient's current phenotype will be reported into the patients' medical record. In the case of positive study findings that may be diagnostic, confirmatory clinical diagnostic testing will be performed on the proband and, when warranted, segregation analysis on other family members. Following this confirmation, a standard clinical diagnostic report will be placed in the patient's medical record, and the nominating physician will be contacted. In the event that an affected family member, such as a sibling, is also a patient of the enrolling hospital system, clinical results will also be returned to that patient's medical record. In the event that clinical genomic sequencing is done by a CLIA accredited laboratory these negative results will be treated as clinical-grade and will be placed in the affected subject's medical record indicating the symptoms used for analysis, the testing done, and the limitations of the results at this time.

**Negative findings:** Although the intention of the study is to return symptom-driven results to the medical record, the clinical report for confirmation of symptom-driven findings may include negative findings of testing. We believe this negative clinical testing result is clinically relevant and should not be withheld as it may be pertinent to patient care and future testing. This testing will preferentially use FDA approved in vitro diagnostics tests where available. In this situation the entirety of the approved test, not just the target variant information will be returned. Similarly, clinical confirmation may be required by an outside laboratory; results reported by this outside laboratory may include variants of unknown significance, genome-wide negative results and/or secondary findings per the clinical lab's testing protocol. These results will be placed in the patient's medical record to reflect the clinical testing ordered. Clinical tests required for confirmation of research results will be charged to this research study.

**Secondary findings:** Whenever possible, this study will not report secondary findings. That is, the laboratory will not intentionally seek to evaluate disease status or predisposition beyond attempting to identify the cause of the child's current health issues. Similarly, other information, identified as a result of the testing but not relevant to the clinical question, such as family relations not being as stated and adult onset conditions will not be returned. In accordance with standard care for clinical laboratories, we will report clinically that no pathogenic results were found related to the patient's specific symptoms. This report will include a list of the symptoms used, the type of testing, and the limitations of the testing. Parents and family members of the affected patient may also be enrolled in this study for the purpose of comparing genetic variants with the affected patient. Similarly to the proband the data will not be evaluated to specifically find carrier information, disease status or predisposition beyond that required to identify the cause of disease in the proband. Only in the event that an immediately life-threatening illness is inadvertently found, such as familial hypercholesterolemia, will results be returned to family members. In this rare event, the family member will be asked to identify a clinician to whom our team may return these results. Genetic inheritance patterns and reoccurrence risks will be included in the patient's results and genetic counsellors will be available to all families enrolled in this study as well as to support their physicians.

As noted above it is the intention of the team to not evaluate the genome for "secondary findings". However it is possible that federal or local rules change more strongly recommending analysis of the genome for other such findings or there is a future research interest in such analysis. The team will therefore seek to identify families that would not want to be contacted in the future to specifically enroll in a study evaluating the return of such secondary findings. If families opt out of such contact, they still may be contacted in the future about primary study questions but will not be approached to consent for future studies about secondary findings return.

**Preliminary Reports –** In instances where a diagnosis suggests an intervention that needs to be implemented

prior to the time required for orthogonal confirmation to potentially avoid morbidity or mortality, the diagnosis will be communicated to the clinical team verbally and a preliminary clinical report will be placed into the medical record. This will be amended or updated when orthologous testing is completed. A preliminary clinical report allows greater access and better adoption of the genomic test information for physicians in EMRs. Additionally, evidence in the literature and internally at RCIGM have shown that data generated from whole genome sequencing (WGS) is equivalent, or even superior in certain instances, to orthogonal methods in terms of sensitivity and specificity. In over 150 diagnoses at RCIGM since inception in 2016, all clinically significant variants have undergone successful orthogonal confirmation. All results are generated in the CAP-accredited, CLIA-certified RCIGM-Clinical Genome Center or collaborating clinically accredited laboratories under the guidance and oversight of the laboratory director. Thus, the preliminary report can be viewed as a preliminary clinical report.

**Incidental** - During the course of the phenotype-driven analysis, if a pathogenic variant is identified that is medically actionable and does not overlap with the patient's reported phenotype, the variant will be reported. Consensus by at least one laboratory director and one RCIGM staff physician must be obtained and documented that the possible benefits of reporting the incidental finding of interest exceeds the potential harms. Clinically significant variants incidentally ascertained in genes associated with a medically actionable condition will be reported as incidental findings if appropriate consent for return of incidental findings has been obtained. Reporting of incidental findings will be reported as stated in the RCIGM clinical laboratory guidelines. Criteria for consideration include, but are not limited to: available evidence of pathogenicity of the variant, medical actionability of the condition of interest, and the benefit:risk ratio of potential medical interventions.

**VUS** - A “variant of uncertain significance” is one for which there is insufficient current evidence to determine if the variant is disease causing (i.e. clinically significant). This may be due to a lack of available evidence supporting pathogenicity or conflicting evidence currently exists. Universally, diagnostic reference laboratories performing whole genome sequencing and whole exome sequencing as commercial diagnostic tests report variants that are classified by the American College of Medical Genetics as “variants of uncertain significance” in genes that are implicated in human disease. Per RCIGM clinical laboratory standard operating procedures, selected VUS’s will be placed in a separate table in the report and verbiage will state that additional testing and clinical correlation will be required to re-classify the variant as clinically significant. Consensus by at least one laboratory director and one RCIGM staff physician must be obtained and documented that the possible benefits of reporting the VUS of interest exceeds the potential harms. This type of reporting is necessary as often the physicians treating the patients are best positioned to conduct follow up testing and further examinations to provide adequate and timely follow-up for a VUS result.

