## **6. SPECIFIC AIMS**

**Specific Aim 1.** Determine if, and by how, much rapid WGS is associated with better outcomes than rapid WES in acutely ill infants. The null hypothesis is that both tests are equivalent. This may occur, for example, if the diagnosis rate is similar or the additional diagnoses from WGS do not alter clinical management.

**Specific Aim 2.** Determine if and by how much rapid WGS is associated with better perceived outcomes in parents of acutely ill infants than rapid WES in acutely ill infants. The null hypothesis is that both tests are

equivalent. In addition, this will be the first study to examine the family-centered outcomes of rapid genomic sequencing, and particularly in Hispanic/Latino families.

**Specific Aim 3.** To compare diagnostic rates, time to diagnosis, and outcomes of rapid genome-wide sequencing compared with historical matched cases who received standard care before genome-wide sequencing was available. The null hypothesis is that genome wide sequencing does not increase diagnosis rate, time to diagnosis or outcomes.

**Specific Aim 4.** To compare diagnostic rates of singleton analysis versus familial analysis (ideally trio) and the cost-effectiveness of each testing method (rapid singleton WGS, rapid singleton WES, rapid trio WGS and rapid trio WES). The null hypothesis is that adding familial sequencing data does not significantly increase diagnostic yield.

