Recently we implemented rapid (3 days) trio WGS at RCIGM. For 4 months we have enrolled acutely ill infants at RCHSD in the protocol “Genomic Biorepository: Protocol for the Collection, Storage, Analysis, and Distribution of Biological Samples, Genomic and Clinical Data (IRB #160468)”. Among 35 families with acutely infants nominated, 29 (83%) were enrolled. The fastest time to diagnosis was 41 hours from blood draw to communication of provisional diagnosis. On average, diagnosis occurred within one week. At time of submission, WGS had been interpreted in 29 families with 30 symptomatic infants, yielding informative data in 28. 15 (53%) of infants received diagnoses. In 14 (50%), the initial diagnosis was by rapid trio WGS. 13 patients had single nucleotide variants and two had structural variants. The leading mechanism of disease was de novo mutations causing dominant genetic disorders. Only two patients received diagnoses prior to completion of rapid trio WGS. Following diagnosis by rapid trio WGS, clinical management changed in 12 (43% of infants tested). Of these, medications were changed in 9 (32%) infants; One infant avoided needless major surgery; Palliative care was initiated in two infants with > \$6M potential healthcare savings. This data replicated our published previous experience at Children’s Mercy Hospital in Kansas City, but was remarkable since enrollment was much broader at RCHSD (namely, the 4 or 5 infants with greatest need of a definitive diagnosis each week).

Additionally, we recently concluded the first randomized, controlled, partially blinded, prospective trial of the 28-day diagnostic yield of rapid trio WGS plus conventional testing versus conventional testing in acutely ill NICU infants (the NIH-funded “NSIGHT” study). While the results are still being evaluated, we found that patients in the control arm of the study also received genetic diagnoses through next-generation sequencing, including WES and WGS, upon unblinding of neonatologists. Similarly, we observed a cross-over rate for compassionate use of WGS of 10%. Nevertheless, we found that the 28-day rate of diagnosis was 5 of 33 (15%) in the control arm and 14 of 32 in the rapid trio WGS arm (44%,  $p < 0.01$ ). Thus, provisionally, we conclude that rapid trio WGS has greater 28-day diagnostic yield than conventional testing. This study was not designed to evaluate clinical utility.

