Rapid WES is ~2-fold less expensive than rapid WGS but has at least one additional day of time to results. There is no data comparing the diagnostic or clinical utility of WES and WGS. WES is the only genome wide sequencing test routinely covered by insurers. In addition, as noted above, all of our rapid WGS cases could theoretically have been detected by WES. Conversely, although WES can analyze the coding regions of nearly all potentially disease causing genes, we believe that WGS is superior, despite its higher costs, due to its ability to detect de novo variants, structural variants (SV), and to interrogate regions of extreme GC content. WGS provides coverage of non-coding variants that can be clinically identified as definitely disease causing. As such, we believe an analysis of diagnostic rates between the two types of tests will show that WGS does in fact provide more diagnoses than WES. However, such increases in diagnoses may not lead to an increase in changes in care as the variants that can be detected only by WGS may be less amenable to specific therapeutic interventions. The primary goal of this study is to evaluate which method provides the optimal outcomes in acutely ill infants with likely genetic diseases. However, we anticipate that we may also – in subsequent amendments – retrospectively re-analyze these samples to determine if WGS or WES has superior ability to yield pharmacogenomic and secondary findings related to childhood-onset conditions. In subsequent amendments, families may potentially be asked for their opinions on receiving such additional testing results, if available, following the discharge of their child. As pharmacogenomics knowledge grows, the need for informed drug choice and dose will be crucial in effectively managing critically ill patients and preventing secondary harm. In particular, we anticipate a future amendment to examine the prevalence of the genetic predisposition to hearing loss following the administration of aminoglycosides, an antibiotic very commonly used in NICUs.

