## **Surveys:**

### **Family Surveys:**

After enrollment into the research study, families will have a brief survey administered assessing their trust in medical providers (see appendix). In-person surveys will be given the option to take the survey on paper independently or administered by research staff verbally. Families for whom a translated survey is not available will have the survey administered using an interpreter. Families will receive two follow-up surveys (see appendix) assessing decisional regret and perceived benefits or harm of testing. The first follow-up survey will be administered within one week of the return of results (including the return of no results), and the second follow-up survey will be administered approximately one year after enrollment. If families are still in the hospital at the time of follow-up, research staff will attempt to meet the families bedside to conduct the survey. For families that are no longer in-patient at the time of follow-up, research staff will attempt to contact families by phone prior to administration of follow-up surveys and families will be offered the choice to decline further

surveys at that time. Barring a verbal decline for further surveys, families will have the choice to take the survey electronically e.g. via a REDCap survey or by phone. Families who chose the electronic survey will be told that if the survey is not completed within 72 hours, the research staff will contact them to conduct the survey by phone, with a possible second contact at a scheduled time.

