### **Clinician Surveys:**

Within one week of the return of results (including the return of no results), clinicians caring for the patient will be asked to complete a brief survey (see appendix) regarding the clinical utility of genomic testing. The surveys may be administered in-person on paper or independently completed on paper or via email messaging to the providers' secured RCHSD or UCSD electronic mail account. Surveys will contain the minimum information required to identify the child in which the testing focuses on. It aims to identify what, if any, changes were made to the immediate management of the patient as a result of testing as well as general utility from the diagnosis. As these surveys are directed at obtaining clinical information about the patients and not assessing the clinicians as research subjects, the clinicians will not be enrolled as a part of this study. A second study of clinicians may be performed under a separate protocol in the future.

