All clinical testing and therapy appropriate to the study participant's care will be continued without disruption during the study. The clinicians are initially blinded to the randomization and will continue all clinical testing regardless of whether rapid genomic sequencing is performed.

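### Does naming the type of test in no-finding reports undermine a trial that calls itself blinded?

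*Combined protocol and SAP*

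**What the plan says.** The Project Title, the Lay Language Summary and the Summary of design each use the word blinded with no role and no end point attached. The one operative statement is in section 15: "The clinicians are initially blinded to the randomization". The rest of that sentence is about clinicians carrying on with their usual testing.

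Under Return of Results, the Secondary findings paragraph describes the report issued when nothing pathogenic is found: "This report will include a list of the symptoms used, the type of testing, and the limitations of the testing". The Primary findings paragraph says that negative results from a CLIA-accredited laboratory go into the medical record "indicating the symptoms used for analysis, the testing done, and the limitations of the results at this time".

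The surveys follow. For clinicians: "Within one week of the return of results (including the return of no results), clinicians caring for the patient will be asked". For families: "The first follow-up survey will be administered within one week of the return of results". The clinician form covers management changes attributed to the test and its general utility. The follow-up family forms cover decisional regret and perceived benefit or harm. Specific Aim 2 rests on the family side: "Determine if and by how much rapid WGS is associated with better perceived outcomes in parents of acutely ill infants".

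**The concern.** A reader who sees the word blinded will assume that subjective ratings were made without knowledge of the arm. Here the report appears to reveal the arm just before those ratings are collected. Section 7 refers to WGS and WES as two types of tests ("an analysis of diagnostic rates between the two types of tests will show that WGS does in fact provide more diagnoses than WES"), so the type of testing in a report most naturally means the randomised arm. The same sentence shows that the team expects WGS to do better. If clinicians share that expectation, their ratings could differ between arms with no true difference in usefulness.

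At stake would be clinicians' perceived utility and, if parents learn the arm, Aim 2. The clinical utility index, which Sample size determination calls a key secondary outcome, could be touched where it depends on a clinician's attribution of a management change. No passage says that staff who abstract the chart are blinded either.

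**Working it through.** The plan gives no figure on this point, so the main check is to set the passages side by side.

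1. **Before results.** The order in the chart has a generic research name (Recruitment, Enrollment and Sample Collection), and both methods have an expected 10-day turnaround (Other Analysis). Both help conceal the arm. Against that, section 7 says WES takes at least one day longer.
2. **At results.** The no-finding report names the type of testing. That this means WGS or WES is the natural reading, but the report template is not supplied, and Patient clinical information uses similar words for genetic tests in general. Whether positive reports name the method is not stated.
3. **After results.** Both surveys are timed from return of results. The filing date of the report relative to the survey is not given, so the order is inferred.
4. **Which outcomes are reached.** Mortality is not a rating. Nothing in the text connects the report wording to QALYs. For management changes, the section 7 pilot reads: "Following diagnosis by rapid trio WGS, clinical management changed in 12 (43% of infants tested". All 12 changes followed a diagnosis, whereas the disclosure shown here concerns infants without one. What remains is clinicians' general-utility rating for no-finding infants. Aim 2 is reached only if parents learn the arm, which the documents do not say.

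**Hypothetical size, for perceived-utility ratings only.** Inputs:
- No-finding share: 100% − 53% = 47% (section 7 pilot).
- Rating rate near 50%, no true difference, one independent rating per infant and complete response: all assumed.
- Shift in the rating among no-finding infants: 3 to 5 percentage points, assumed, with no basis in the documents.
- Arm sizes: 125 (half of the roughly 250 infants expected by September 2019), 325 and 500 (section 10).

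Formulas: SE = √(2 × 0.25 / n); bias = share × shift; two-sided error = P(|Z + bias/SE| > 1.96).

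Bias = 0.47 × 0.03 = 0.0141, or 0.47 × 0.05 = 0.0235.

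| n per arm | SE | error, 3 points | error, 5 points |
|---|---|---|---|
| 125 | 0.0632 | 5.6% | 6.6% |
| 325 | 0.0392 | 6.5% | 9.2% |
| 500 | 0.0316 | 7.3% | 11.5% |

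A 1-point shift gives 5.1% to 5.3% across these sizes. Doubling the error to 10% needs a shift of 8.8, 5.4 or 4.4 points respectively. Diagnosis rates elsewhere in section 7 run from 44% to 58%, so the no-finding share runs from 42% to 56%. Over that range the 3-to-5-point results are 5.5% to 7.3%, 6.2% to 11.0% and 6.8% to 14.4%. With 80% response at the 47% share they fall to 5.5% to 6.3%, 6.2% to 8.3% and 6.8% to 10.2%.

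The table answers only an if-question. The survey form is not supplied, so a yes/no rating near 50% is a guess. Section 12 also allows several clinicians to rate one infant, which the model ignores.

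**The case for a change.** The strongest case for a change is that the label is wrong and correcting it costs almost nothing. Section 7 describes the team's own earlier trial as only partly blinded, so the qualified term was available. The CLIA condition on negative reports looks routine, because the Preliminary Reports paragraph says all results come from certified or accredited laboratories. Send-out exome testing (Other Analysis) means that a laboratory name could also give the arm away. Bias of this kind does not shrink with enrolment, so the error inflation grows toward the maximum sample.

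Much of this stands. The word is unqualified, and clinicians' ratings for no-finding infants should not be read as blinded. But each remedy falls short of a change worth making:

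- **Stating who is blinded and until when.** This records what section 15 already half says. It alters no estimate, test or conclusion, and an analyst writing the report would supply it. The end point would have to come from the sponsor, since no passage gives one. The section 15 sentence also speaks of whether sequencing is done at all, which fits a sequenced-versus-unsequenced trial better than this one.
- **Asking respondents whether they knew the test.** Awareness arises after randomisation, so the answer can only be described, not adjusted for.
- **Redacting chart extracts before coding.** This means two staff roles per extract for up to 1,000 infants, to address a lack of blinding inferred from silence while the data collection sheet is in an appendix not supplied. Variant type could still reveal the arm, and redaction would not undo any change in clinician behaviour.

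Masking the report itself would cut against a stated choice. The Negative findings paragraph treats a negative result as relevant to care and later testing. A negative genome and a negative exome also carry different information, so some difference in how clinicians value them may be part of the real contrast between arms.

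**Conclusion.** No change to the plan. The blinding that the protocol describes is a limited one: clinicians do not know the arm at first, while routine testing continues. Disclosure at reporting is deliberate, and the unqualified label is imprecise wording that a competent analyst will resolve by presenting the clinician ratings, and the family ratings if parents know the arm, as unblinded once results are returned.

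What is reasonably established is narrow: clinicians' general-utility ratings for infants without a finding are probably made with the arm known. That rests on reading the type of testing as WGS or WES, and on the report reaching the clinician before the survey. Effects on Aim 2, the clinical utility index and chart coding are not shown. No size or direction can be taken from the documents, and the error rates above are hypothetical.
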